Normality was tested using the Shapiro-Wilk test where significance ($p < 0.05$) indicated a non-normal distribution. Both LVM and LVM/BSA violated the Shapiro-Wilk test of normality. Simple bivariate comparisons between groups were made using unpaired t-tests for normally distributed variables, and Mann-Whitney tests when normality was violated. Effect sizes for bivariate comparisons were estimated using Cohen's d with 95% confidence intervals. Spearman's rank correlations coefficient (ρ) was used to examine relationships within each group and for all participants and variables of interest vs. LVM and LVM/BSA. ANCOVA tests were used to examine LVM and LVM/BSA compared between groups while statistically controlling for covariates of interest. LVM and LVM/BSA were logarithmically transformed prior to the ANCOVA investigations. The ANCOVA models were as follows. In model 1, age, SBP and sex were selected as common participant characteristic covariates that impact LVM and LVM/BSA. Model 2 accounted for the days per week of moderate-intensity exercise. Model 3 accounted for the days per week of vigorous-intensity exercise. Model 4 covariates included EDV and TPR as indices of preload and afterload. A significant probability value ($p < 0.05$) within the ANCOVA model for FHH status was interpreted as finding between-group differences when statistically controlling for the covariate variables. A lack of FHH significance in the model was interpreted as FHH status does not impact LVM or LVM/BSA independently of the covariate variable(s) within the model. Data is expressed as mean \pm SD. The alpha level for significance was set at $p < 0.05$. All statistical tests were performed using JASP version 0.14.1 (University of Amsterdam, Amsterdam, The Netherlands).

Data Availability

Data is available on the Montclair State University Digital Commons website at:
<https://digitalcommons.montclair.edu/data/10>

References

1. Du Bois D. Clinical Calorimetry. *Arch Intern Med.* 1916;XVII:863.
<http://linkinghub.elsevier.com/retrieve/pii/S089473170245599X>

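### A non-significant FHH term is read as proof of no independent FHH effect, with no adjusted interval or margin behind it

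*Combined protocol and SAP*

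**What the plan says.** The Statistical Analysis section sets a two-way rule for the FHH term in each ANCOVA. A p-value below 0.05 "within the ANCOVA model for FHH status was interpreted as finding between-group differences when statistically controlling for the covariate variables". Otherwise, a "lack of FHH significance in the model was interpreted as FHH status does not impact LVM or LVM/BSA independently of the covariate variable(s" in that model. There are four models (age, SBP and sex; moderate-exercise days; vigorous-exercise days; EDV and TPR), each applied to LVM and LVM/BSA.

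The only interval estimates in the plan belong to the unadjusted comparisons: "Effect sizes for bivariate comparisons were estimated using Cohen's d with 95% confidence intervals". On the scale of the models it says "LVM and LVM/BSA were logarithmically transformed prior to the ANCOVA investigations". The section also reports that "Both LVM and LVM/BSA violated the Shapiro-Wilk test of normality", so at least part of the analysis had been done when the text was written.

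The document states no sample size, power, smallest difference of interest, equivalence margin or equivalence test. It describes no adjusted difference or ratio, and no confidence interval for the FHH term.

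**The concern.** The second branch of the rule turns a failure to reject into a positive finding of no effect. A p-value of 0.05 or more can come from a negligible effect or from an imprecise estimate of a sizeable one, and the p-value alone cannot tell these apart. An interval for the adjusted effect could, but none is planned. The Cohen's d intervals do not fill the gap: they are unadjusted, and since the log transform is stated only for the ANCOVA, they appear to be on a different scale from the models.

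The conclusion at stake is the one named in the document's title, the impact of FHH on left ventricular mass. Because the four models adjust for different covariates, readers will compare their verdicts. A covariate that overlaps with FHH can widen the standard error and push p above 0.05 with the FHH estimate unchanged. The rule would then report a difference in one model and no impact in another although the estimated difference is the same. The p < 0.05 branch is not in dispute here.

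**Working it through.** The plan gives no figure to reproduce. From the document come alpha = 0.05 (taken as two-sided, as in an ANCOVA F test), the log-scale outcomes, the two FHH groups, and the number of covariates per model: k = 3 in model 1, 1 in models 2 and 3, 2 in model 4. Group size, residual SD, effect size and covariate overlap are not given; every value used for them below is an assumption.

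**1. Number of verdicts.** 4 models × 2 outcomes = 8 FHH tests under the rule.

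**2. Boundary result (needs no n or SD).** Let b be the adjusted log ratio and SE its standard error. At p = 0.05, t_crit × SE = b, so the 95% interval on the log scale is b ± b, that is 0 to 2b. Back-transformed, it runs from 1.00 to ratio². For an observed ratio of 1.10 the upper limit is 1.10² = 1.21. The 10% is a chosen example; the identity is general.

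**3. How often the rule says no impact when an effect exists (illustration).** SE = SD × √(2/n) / √(1 − R²), where n is per group and R² is the share of FHH variance explained by the covariates; df = 2n − 2 − k; probability of p ≥ 0.05 from the non-central t distribution with non-centrality ln(true ratio)/SE. Example: n = 50, R² = 0, true ratio 1.10, so ln(1.10) = 0.0953. With SD 0.18, SE = 0.18 × √(2/50) = 0.036, non-centrality 2.65, probability 25%. With SD 0.26, SE = 0.052, non-centrality 1.83, probability 56%. Ranges below are for residual log SD 0.18 to 0.26:

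| True effect, R² | n = 20 | n = 30 | n = 50 | n = 100 |
|---|---|---|---|---|
| +5%, R² = 0 | 87–91% | 82–89% | 73–85% | 52–74% |
| +10%, R² = 0 | 63–80% | 48–71% | 25–56% | 4–27% |
| +10%, R² = 0.2 | 69–83% | 56–76% | 35–63% | 8.5–36% |
| +15%, R² = 0 | 33–62% | 16–47% | 3–24% | 0–3% |

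Moving k from 1 to 3 changes these by about 0.1 percentage point.

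**4. Same estimate, different verdict (illustration).** Fix the ratio at 1.10, n = 50 per group, residual SD 0.22, k = 3, df = 95. With R² = 0, SE = 0.22 × √(2/50) = 0.044, t = 0.0953/0.044 = 2.17, p = 0.033, interval 1.01–1.20. With R² = 0.1, 0.2 and 0.3, p = 0.043, 0.056 and 0.073; at 0.3 the interval is 0.99–1.22. The verdict changes between 10% and 20% overlap while the estimate stays at 1.10.

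**The case against.** The inferential error itself is hard to defend. The objections are to its weight, the overlap example and the size of the remedy.

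- **Harm is conditional.** The documents show no results, so whether a negative conclusion was drawn is unknown. The Data Availability section points to a public deposit; if it holds the model variables, others could compute the intervals. Both points stand, but neither corrects a written rule that yields an unsupported conclusion when followed exactly.
- **The overlap example is one-sided.** It holds the residual SD at 0.22, although covariates chosen because they affect LVM should reduce it. This is right. With the same inputs, 20% overlap together with 20% of within-group outcome variance explained brings p back to 0.033, because the factors √(1 − 0.2) cancel in the SE. At 20% overlap and 30% explained, p is 0.023. Adjustment can move p either way. That limits the example to showing what can happen; it still shows that the verdict can depend on precision alone.
- **The starting point is not in the plan.** No unadjusted log-scale model is specified, so under the rule a switch could arise only between models 1 to 4. This is correct.
- **The probabilities are mostly assumption.** They run from near 0 to 91%. True; only the boundary identity is free of assumed inputs.
- **Studying the change in the ratio goes further than needed.** It answers a question about attenuation that the plan does not set as an aim. In model 4, EDV and TPR may lie on the pathway from FHH to LVM, so reading that change needs further assumptions. This is fair: that step is optional.

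**Conclusion.** The concern holds and must be fixed. As written, the plan licenses a claim of no independent FHH effect from p ≥ 0.05 alone, for all eight model-by-outcome tests, and nothing elsewhere in the document supports that reading. This rests on the wording of the rule and needs no assumption about the data. The boundary result shows the scale: an observed +10% at p = 0.05 leaves +21% inside the interval. The error probabilities depend on assumed group sizes, SDs and effects. In a large study the error would matter less, but the plan states no size by which to judge that. Whether a negative conclusion was in fact drawn cannot be seen.

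**What to change.** Replace the sentence on non-significance with wording such as:

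> For each model and outcome, the adjusted FHH ratio of geometric means, back-transformed from the log model, is reported with its 95% CI, beside the unadjusted log-scale ratio in the same participants with its 95% CI. A p-value of 0.05 or more is described as no independent difference shown, with the data compatible with ratios from X to Y.

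Allow a statement of no meaningful independent impact only when the interval lies within a justified margin. Since normality results are already reported, a margin set after the data were analysed must be disclosed as post hoc.

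Optionally, if the authors wish to say that covariates account for an FHH difference, base that on the change in the ratio between the unadjusted and adjusted models, with an interval for the change (for example a participant-level bootstrap), not on whether p crosses 0.05. For model 4, state the assumptions about EDV and TPR as possible intermediates.

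Cost: no new data and no change to the four fitted models. The work is rewording, back-transformed coefficients with intervals, one unadjusted log-scale fit per outcome, and a bootstrap only if the change in ratio is interpreted. The price is weaker negative statements and a post hoc caveat on any margin chosen now.
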